#### **4. TREATMENT PLAN**

##### **4.1 Study Design**

This is a 2-arm phase II study with each of the 2 tumor types (melanoma, NSCLC) will be treated on a different arm. After establishing eligibility criteria, for patients with melanoma the investigator will determine at least one lesion that requires local therapy (surgical resection or LITT) based on size, location, and/or risk of hemorrhage; this will be considered the “surgical lesion”. All other eligible brain lesions will be considered “clinically evaluable lesions” and will be followed by modified RECIST (mRECIST) criteria to determine best response. Patients with NSCLC are not required to have a “surgical lesion” but must have at least one “clinically evaluable lesion” in the CNS. After obtaining informed consent, patients with melanoma will undergo local therapy to the study lesion (resection or LITT) and tumor tissue will be studied for B7-H1 (PD-L1) and other biomarkers as potential predictors of sensitivity to MK-3475, although it should be noted that the presence of a biomarker is not necessary for patients with melanoma to go on trial. Expression of PD-L1 will be determined both by Merck and by the Yale team. Patients on the NSCLC arm in Cohort 1 are required to have formalin-fixed, paraffin-embedded tumor tissue available for biomarker analysis, and those who do not have PD-L1 expression will be ineligible for treatment. Patients with NSCLC who test negative for PD-L1 expression or are unevaluable for PD-L1 expression will be eligible for Cohort 2. PD-L1 expression will be determined by the Merck assay. This will be followed by treatment with MK-3475 10mg/kg IV every 2 weeks. Each cycle consists of 2 weeks of treatment. Day 1 of the study will be defined as the first day a patient receives MK-3475.

An MRI of the brain will be obtained after 2 cycles (4 weeks) of systemic therapy for patient safety (i.e., to confirm there is no imminent risk in the case of progressing lesion or new/worsening edema). Patients with new symptoms from CNS lesions, progressing lesions or worsening edema may be taken off study and treated with local therapy to the brain metastases. An efficacy evaluation will then be performed after 4 cycles (8 weeks) including MRI of the brain and CT scans of systemic disease. Brain metastasis response will be determined using modified RECIST (mRECIST) criteria. The next MRI of the brain will be obtained after 8 cycles (week 16) and then

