#### 4.7 Duration of Therapy

In the absence of treatment delays due to adverse event(s), treatment may continue for up to 2 years or until one of the following criteria applies:

1	Disease progression (see Section 4.8)
2	Symptomatic deterioration of health status without objective evidence of disease progression. Every effort should be made to document objective progression of disease in such cases.
3	Imminent risk in the case of progressing lesion or new/worsening edema seen on brain MRI
4	Unmanageable toxicity most probably attributed to MK-3475 (see Table 2)
5	Development of intercurrent illness limiting the ability to comply with study or the development of uncontrolled concurrent illness that prevents further administration of treatment or confound the ability to interpret data
6	General or specific changes in the patient's condition rendering the patient unacceptable for further treatment in the judgment of the investigator
7	Patient request for discontinuation, patient withdrawal from study, or patient lost to follow up
8	Development of neurologic or systemic complications following local therapy to any lesion
9	Death
10	Study termination by sponsor

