DCT scan of the chest/abdomen/pelvis should be performed every 8 weeks +/- 5 days of therapy. Response evaluation is performed using RECIST 1.1 and ir-RECIST

ECT scan of the chest/abdomen/pelvis and brain MRI should continue every 8 weeks (+/- 5 days) until progression, withdrawal of consent, death, lost to follow-up, or start of a subsequent anti-cancer therapy

FFor patients who will undergo local therapy on trial, investigators must identify “surgical lesion(s)” and “clinically evaluable lesion(s)”. Brain MRI must be done within 28 days of intervention and should be repeated if more than 28 days will have lapsed by the start of systemic therapy. For patients who previously underwent local therapy to a brain lesion and have tumor tissue available for analysis, only identification of “clinically evaluable lesion(s)” is necessary.

GBrain MRI on Day 1 of Cycle 3 to assess patient safety only; response assessment should not be performed. MRIs should be done with perfusion, if possible.

HBrain MRI should continue every 8 weeks (+/- 5 days) along with systemic evaluation. CNS response evaluation is performed using mRECIST and ir-mRECIST criteria. Perfusion will be done, if possible.

I Can be done at screening or any time prior to Cycle 1 Day 1 dosing

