## **10. MEASUREMENT OF RESPONSE**

Response will be evaluated after 8 weeks of systemic therapy and then every 8 weeks thereafter. The purpose of the 4 week scans is to determine safety. If symptoms develop or clinical deterioration occurs, patients may be imaged prior to the pre-specified time points for imaging. All responses must be confirmed by repeat imaging at least 4 weeks following initial documentation of objective response.

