### **10.5 Progression-Free Survival (PFS)**

PFS is defined as the time from initiation of study drug until the first documented, confirmed progression of clinically evaluable brain metastases based on mRECIST criteria, systemic disease based on RECIST criteria, or death. If there is progression of disease that is then confirmed on a follow up scan at least 4 weeks later, the initial date of documented progression should be used in the PFS analysis.

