**11.3 Analytic Plan for Secondary Objectives:**

- (1) Best overall response rate (ORR) is defined as the percentage of patients who experience a CR or PR in any metastases (clinically evaluable cerebral or systemic) as determined by mRECIST criteria in the brain or RECIST criteria in the body. The proportion of patients

with an ORR will be calculated with a 95% confidence interval. A similar analysis will be performed using ir-mRECIST and ir-RECIST.

- (2) B7-H1 (PD-L1) expression and other potential biomarkers will be correlated to clinical endpoints. Exploratory, hypothesis-generating analyses will be performed.
- (3) Progression-free survival will be calculated as the time from start of MK-3475 to progression (using mRECIST criteria for brain lesions and RECIST criteria for systemic disease) or death. Overall survival will be calculated as the time from start of MK-3475 to death. Patients who do not meet the endpoint will be censored at the date of last follow-up. PFS and OS will be determined separate for each arm and median survival will be estimated by using Kaplan-Meier methodology
- (4) Safety and toxicity will be assessed using CTC v4.0 criteria. All participants who receive any amount of study drug will be evaluable for toxicity.

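### A progressing brain lesion on the week-4 MRI can end participation, but no rule makes it a PFS event, so some of the earliest CNS progressions can enter PFS only at death or as censored times

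*Combined protocol and SAP*

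**What the plan says.** **Removal at week 4.** Section 4.1, describing the MRI after two cycles, says: "Patients with new symptoms from CNS lesions, progressing lesions or worsening edema may be taken off study and treated with local therapy". Section 4.7 gives a matching reason for stopping treatment, "Imminent risk in the case of progressing lesion or new/worsening edema seen on brain MRI", as item 3, separate from disease progression, which is item 1.

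**Scoring of that scan.** Footnote G of the study calendar (section 6.4) reads: "Brain MRI on Day 1 of Cycle 3 to assess patient safety only; response assessment should not be performed". Section 10 agrees: "The purpose of the 4 week scans is to determine safety", and "Response will be evaluated after 8 weeks of systemic therapy and then every 8 weeks thereafter".

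**PFS.** Section 10.5: "PFS is defined as the time from initiation of study drug until the first documented, confirmed progression of clinically evaluable brain metastases", or of systemic disease, or death. A progression confirmed at least 4 weeks later is dated to the first scan that showed it. Section 11.3 begins "Progression-free survival will be calculated as the time from start of MK-3475 to progression (using mRECIST criteria for brain lesions" and does not repeat the confirmation requirement. It censors patients without an event at last follow-up.

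**After removal.** Under section 6.3 there is a visit 28 ± 7 days after the last dose, and CT and brain MRI continue every 8 weeks until progression or the start of another anti-cancer therapy, among other reasons. Survival contacts continue every 3 months.

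**Local therapy.** Under section 5.2 a locally treated lesion is no longer evaluable. If it makes up more than 25% of the target lesions, this is progressive disease. An additional response evaluation treats anyone needing local therapy on study as progressing at that time.

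**The concern.** Early growth in the brain is a failure this trial particularly needs to record. Three rules that are each reasonable do not fit together. The week-4 scan can end participation, it is not assessed for response, and PFS recognises only mRECIST progression or death. Progressive disease is one of the mRECIST categories in section 10.1, so a site can fairly read the ban on response assessment as covering it.

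If other therapy follows, scheduled scans may stop and a treated lesion can no longer supply the confirming scan. Because censoring is at last follow-up and not at the last tumor assessment, survival contacts can keep such a patient in the PFS risk set as progression-free. Each arm is a single-arm estimate for its disease, so the error has no control group in which to cancel.

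**Working it through.** **1. What each rule does with a patient removed at week 4 for CNS growth**

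| Situation after removal | Rule | Enters PFS as |
|---|---|---|
| No new therapy, scans continue | 6.3 | Can be scored at about week 8 |
| Local therapy to more than 25% of target lesions | 5.2 | Progression, if 5.2 is carried into PFS (not stated) |
| Other local therapy while on study | 5.2, additional evaluation | Progression in a response evaluation; PFS not named |
| Already off study, then local or other new therapy | None explicit | Death, or censored at last follow-up |

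For one treated lesion the share of targets is 1/1 = 100%, 1/2 = 50%, 1/3 = 33%, 1/4 = 25%, 1/5 = 20%. The 25% rule is met with one to three targets and not with four or five. A new lesion is not a target lesion, so treating it does not trigger that rule; only the additional evaluation reaches it.

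**2. Inputs for size**

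The documents give no PFS target and no week-4 removal rate, so there is no stated figure to reproduce. Assumptions:
- Share removed at week 4 and never scored: f = 5% or 10%.
- Others: exponential PFS, median 4 months. Section 2.5 reports a median of up to 4 months with chemotherapy in NSCLC.
- Removal to death: exponential, median 4 months (section 2.5 reports historical survival of about 2.5 to 4 months) or 12 months (a longer assumed value).
- Scans every 8 weeks = 1.84 months; week 4 = 0.92 months.

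**3. Six-month PFS**

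The last scan before 6 months is at 5.52 months. PFS in the others there is 2^(−5.52/4) = 0.384.

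- Scored at week 4: (1 − f) × 0.384.
- Never scored, counted at death: (1 − f) × 0.384 + f × 2^(−(6 − 0.92)/d), where d is the median from removal to death.
- The overstatement is the last term. The survival factor is 0.415 for d = 4 and 0.746 for d = 12.

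| f | Scored | Never scored, d = 4 | Never scored, d = 12 | Overstatement |
|---|---|---|---|---|
| 5% | 36.5% | 38.6% | 40.2% | 2.1 to 3.7 points |
| 10% | 34.6% | 38.7% | 42.0% | 4.1 to 7.5 points |

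If the removed patients are instead censored at week 4, the estimate is 0.384 whatever f is: 3.8 points too high at f = 10%.

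**4. Median PFS**

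At the 3.68-month scan PFS in the others is 2^(−3.68/4) = 0.529. With f = 10% scored, 0.9 × 0.529 = 0.476, so the median is 3.68 months. Unscored, the curve stays above 0.5 until the next scan and the median is 5.52 months. With f = 5% scored, 0.95 × 0.529 = 0.502, and the median is 5.52 months either way. At f = 10% with the others' median at 2.5, 3, 4.5 or 5 months, the two medians coincide. The jump of one scan interval reflects where 0.529 happens to fall.

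**5. Late scoring versus no scoring**

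In a separate simulation (1,500 runs per setting, 10% to 30% removed), scoring these patients at week 8 instead of week 4 moved the mean estimated median by no more than about 0.1 week at N = 44 and by at most 0.8 week at N = 20. The harm comes from progressions never scored.

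**The case against.** **Footnote G bars response assessment and does not expressly forbid recording progression.** This stands as a reading. Section 10.5 is not limited to scheduled scans, and section 11.4.2 requires every patient to be given a category. A reader might infer that the plan forces week-4 progressions to go unscored; the text does not say so. But the lenient reading still leaves the event and its date undefined, and two sites could score identical patients differently.

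**Section 5.2 covers most cases.** It covers more than the 25% rule alone, because the additional evaluation has no lesion-share condition and so reaches new lesions and one of five targets when treated on study. It is, however, a response evaluation that does not mention PFS, and patients already off study may fall outside it.

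**Later scans will catch the progression.** They can for patients who start no new therapy, with little effect on the estimate. Whether local brain therapy counts as subsequent anti-cancer therapy for stopping scans is not stated.

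**PFS is secondary and descriptive.** True: it has no target or power, and the go/no-go decision rests on the brain metastasis response rate. This limits the weight of the point. It does not remove it, since PFS is one of the four efficacy measures named in section 1.

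**Conclusion.** The concern holds as a gap in PFS scoring. Following the plan as written can leave some week-4 CNS progressions unscored, and when it does, PFS reads too long.

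On the stated assumptions, six-month PFS is overstated by about 4 to 7 points with 10% removed and never scored, and by about 2 to 4 points with 5%. These are upper figures for a given removal share, because any patient picked up through section 5.2 or a later scan shrinks the effect. Only the direction is firm.

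Two stronger readings are not supported. A reader might infer a shift of nearly two months in median PFS (3.68 to 5.52 months); that depends on the scan grid and vanishes at 5% removed or with a slightly different median. A reader might also infer that the primary endpoint is inflated. It is not: section 11.4.2 counts categories 4 to 9, which include progression, early death and unknown, as failures, so the final brain metastasis response rate is unaffected.

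**What to change.** Reconcile footnote G and section 10 with sections 5.2, 10.5 and 11.3 by stating that:

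1. The week-4 MRI is not used to declare response but is measured by mRECIST.
2. mRECIST progression on it (at least a 20% increase in the sum of diameters, or a qualifying new lesion) is a PFS event dated to that MRI if later confirmed, or if confirmation is impossible because the patient left the study or received local brain therapy or new anti-cancer therapy.
3. Other patients without an event are censored at the last evaluable tumor assessment.
4. A sensitivity analysis counts every week-4 removal or local therapy prompted by CNS findings, including edema alone, as an event.

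The event in item 2 is the measurement and not the decision to remove. Patients with equal, confirmed growth who stay on treatment are then scored alike, and edema alone, which is not mRECIST progression, stays out of the main analysis.

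The cost is a few sentences and a few more lesion measurements on a scan already being done. PFS will read slightly less favourably, and some pseudoprogression may be counted as events. The clinical decision at week 4 stays as it is.

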## 7 ADVERSE EVENTS: LIST AND REPORTING REQUIREMENTS

### 7.1 Safety Analysis

Safety will be analyzed for patients treated in this study. All patients who receive any amount of study drug will be evaluable for toxicity.

At each visit, a brief focused history will be obtained and any indication of treatment- related toxicity will be evaluated by appropriate examination and/or laboratory/radiographic studies.

Safety analyses will include summaries of adverse event rates and changes in laboratory results, as well as number of CTCAE (v4.0) toxicity grades for both laboratory and non-laboratory data.

The evaluation period should extend from date of first treatment until 90 days from discontinuation of treatment or until resolution from all acute toxicities associated with the drug administration.

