#### 4.5 MK-3475 Dosage and Administration

##### Trial Treatments

Drug	Dose/Potency	Dose Frequency	Route of Administration	Regimen/Treatment Period
MK-3475	10 mg/kg	Q2W	IV infusion	Day 1 of each cycle

AEs associated with pembrolizumab exposure may represent an immunologic etiology. These immune-related AEs (irAEs) may occur shortly after the first dose or several months after the last dose of pembrolizumab treatment and may affect more than one body system simultaneously. Therefore, early recognition and initiation of treatment is critical to reduce complications. Based on existing clinical trial data, most irAEs were reversible and could be managed with interruptions of pembrolizumab, administration of corticosteroids and/or other supportive care. For suspected irAEs, ensure adequate evaluation to confirm etiology or exclude other causes. Additional procedures or tests such as bronchoscopy, endoscopy, skin biopsy may be included as part of the evaluation. Based on the severity of irAEs, withhold or permanently discontinue pembrolizumab and administer corticosteroids. Dose modification and toxicity management guidelines for irAEs associated with pembrolizumab are provided in Table 2.

Table 2. Dose Modification Guidelines for Drug-Related Adverse Events

General instructions:				

 
1. Corticosteroid taper should be initiated upon AE improving to Grade 1 or less and continue to taper over at least 4 weeks.
 
2. For situations where pembrolizumab has been withheld, pembrolizumab can be resumed after AE has been reduced to Grade 1 or 0 and corticosteroid has been tapered. Pembrolizumab should be permanently discontinued if AE does not resolve within 12 weeks of last dose or corticosteroids cannot be reduced to <math>\leq 10</math> mg prednisone or equivalent per day within 12 weeks.
 
3. For severe and life-threatening irAEs, IV corticosteroid should be initiated first followed by oral steroid. Other immunosuppressive treatment should be initiated if irAEs cannot be controlled by corticosteroids.
 
				
Immune-related AEs	Toxicity grade or conditions (CTCAEv4.0)	Action taken to pembrolizumab	irAE management with corticosteroid and/or other therapies	Monitor and follow-up

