**6.3 Follow-up Visits**

All patients who discontinue the study treatment will have a follow up visit at Day 28 ±7 days from the last study treatment.

- 1) History and physical examination
- 2) Measurement of height, weight and vital signs (including blood pressure, heart rate, respiratory rate, oxygen saturation, and temperature).
- 3) Performance status evaluation
- 4) Review concomitant medications
- 5) Adverse events assessment
- 6) CBC with differential, serum chemistry (Na, K, Cl, CO2, BUN, creatinine, glucose, calcium), magnesium, phosphate, liver function tests (albumin, total protein, alkaline phosphatase, total and direct bilirubin, ALT, AST), LDH
- 7) Tumor assessment with CT scan of the chest/abdomen/pelvis and brain MRI with perfusion, if possible, should continue every 8 weeks (+/- 5 days) until progression, withdrawal of consent, death, lost to follow-up, or start of a subsequent anti-cancer therapy

All patients who discontinue early or who complete the study treatment period will be followed for survival. Survival follow-up information will be collected via telephone calls, patient medical records, and/ or clinic visits every 3 months +/- 14 days until death, loss to follow-up or study termination. All patients will be followed for survival unless the patient requests to be withdrawn from follow-up. If the patient withdraws from study treatment but not from follow-up, the study staff may use a public information source to obtain information about survival status.

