**6.4 STUDY CALENDAR (Table 7).**

Screening evaluations are to be conducted within 7 days prior to start of systemic therapy. Scans must be done 28 days prior to the start of systemic therapy. In the event that the participant’s condition is deteriorating, laboratory evaluations should be repeated within 48 hours prior to initiation of the next cycle of therapy.

All assessments must be performed prior to administration of any study medication. All study assessments and medications should be administered within ± 3 days of the protocol-specified date, unless otherwise noted.

	Screening Visit	On-Study Visits	Follow-up Visit	Long Term Follow-up
--	-----------------	-----------------	-----------------	---------------------

	Day -28 to -1	Day 1 of each Cycle	Day 1 Cycle 3 (after 4 weeks +/- 5 days of therapy)	Day 1 Cycle 5, and every 8 weeks, thereafter	Day 28 +/- 7 days from last study treatment	Every 3 months +/- 14 days after the follow-up visit
Informed Consent	X					
History/Physical Exam	X	X			x	
Height/Weight/Vital Signs A	X	X			x	
Performance Status	X	X			x	
CBC, serum chemistry, liver function tests, LDH B	X	X			x	
PT/INR (for patients on warfarin)	X	X			X	
Carbamazepine or Phenytoin level (for patients on drug)	X	X			x	
TSH, free T3, free T4	X			x		
NSCLC patients: Determination of PD-L1 expression in tumor (Cohort 1 only)	X					
Plasma for correlative studies	X I			x		
Obtain extracerebral tumor specimen for correlative studies (Refer to Section 6.1 and 9.2)	X					
Pregnancy Test C	x					
CT chest/abdomen/pelvis	x			X D	X E	
Brain MRI	x F		X G	X H	X E	
Selection of "surgical lesion(s)" and "clinically evaluable lesion(s)"	x					
Pulmonary Function Tests – NSCLC patients only	X					
Review concomitant medications		X			x	
Adverse events assessment		X			x	
Administration of MK-3475		X				
Survival Follow-up						X

AIncludes blood pressure, heart rate, respiratory rate, oxygen saturation, and temperature. Height at Visit 1 only.

BIncludes CBC with differential, serum chemistry (Na, K, Cl, CO2, BUN, creatinine, glucose, calcium), magnesium, phosphate, liver function tests (albumin, total protein, alkaline phosphatase, total and direct bilirubin, ALT, AST), LDH

CPregnancy test (serum or urine) is required for women of childbearing potential only.

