### 7.5.4 Reporting to Merck

Any serious adverse event, or follow up to a serious adverse event, including death due to any cause other than progression of the cancer under study that occurs to any subject from the time the consent is signed through 90 days following cessation of treatment, or the initiation of new anti-cancer therapy, whichever is earlier, whether or not related to Merck product, must be reported within 24 hours to (Investigator-Sponsor) and within two (2) working days to Merck Global Safety (GS).

Non-serious Events of Interest will be forwarded to Merck GS and will be handled in the same manner as SAEs.

Additionally, any serious adverse event, considered by an investigator who is a qualified physician to be related to Merck product that is brought to the attention of the investigator at

any time outside of the time period specified in the previous paragraph also must be reported immediately to the Investigator-Sponsor and to Merck.

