#### **7.5.5 Duration of Reporting of SAEs**

From the administration of first treatment until 90 days (unless otherwise specified) subsequent to last treatment or withdrawal of subject, new onset adverse events will be captured. Follow-up and reporting of these events will follow the same procedure as for AEs observed during the study period. In addition, any unexpected Serious Adverse Event that occurs more than 90 days after drug administration but is possibly, probably or definitely attributed to drug administration will be recorded and reported.

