## **7.8 Events of Clinical Interest**

Selected non-serious and serious adverse events are also known as Events of Clinical Interest (ECI) and must be reported to the Sponsor.

For the time period beginning when the consent form is signed until treatment allocation/randomization, any ECI, or follow up to an ECI, that occurs to any subject must be reported within 24 hours to the Sponsor if it causes the subject to be excluded from the trial, or is the result of a protocol-specified intervention, including but not limited to washout or discontinuation of usual therapy, diet, placebo treatment or a procedure.

For the time period beginning at treatment allocation/randomization through 30 days following cessation of treatment, any ECI, or follow up to an ECI, whether or not related to the Sponsor's product, must be reported within 24 hours to the Sponsor, either by electronic media or paper.

Electronic reporting procedures can be found in the EDC data entry guidelines. Paper reporting procedures can be found in the Investigator Trial File Binder (or equivalent).

Events of clinical interest for this trial include:

- an overdose of Merck product, as defined in Section 7.2.1 – Definition of an Overdose for This Protocol and Reporting of Overdose to the Sponsor, that is not associated with clinical symptoms or abnormal laboratory results.
- an elevated AST or ALT lab value that is greater than or equal to 3X the upper limit of normal and an elevated total bilirubin lab value that is greater than or equal to 2X the upper limit of normal and, at the same time, an alkaline phosphatase lab value that is less than 2X the upper limit of normal, as determined by way of protocol-specified laboratory testing or unscheduled laboratory testing.\*

\*Note: These criteria are based upon available regulatory guidance documents. The purpose of the criteria is to specify a threshold of abnormal hepatic tests that may require an additional evaluation for an underlying etiology.

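### Adverse events are to be evaluated and captured to 90 days after treatment, but the last scheduled adverse-event assessment is at day 28 ± 7

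*Combined protocol and SAP*

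**What the plan says.** **Window promised.** Section 7.1 (Safety Analysis) sets the evaluation period "from date of first treatment until 90 days from discontinuation of treatment", or until acute drug toxicities have resolved. Section 7.5.5 uses the same span, "From the administration of first treatment until 90 days" after the last treatment or withdrawal, and says that in it "new onset adverse events will be captured". Despite its title, which refers to SAEs, that sentence covers all new AEs.

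**Collection scheduled.** Section 6.3 states: "All patients who discontinue the study treatment will have a follow up visit at Day 28", with a margin of 7 days either way, and AE assessment is on that visit's list. The next column of Table 7 is "Every 3 months +/- 14 days after the follow-up visit", and the only row marked in it is survival. Section 6.3 describes those contacts in the same way. CT and brain MRI continue 8-weekly after treatment until progression, new therapy or another listed end, without an AE item.

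**Reporting rules.** Section 7.5.4 requires serious events to be reported "from the time the consent is signed through 90 days following cessation of treatment", cut short if new anti-cancer therapy starts earlier. It adds that non-serious Events of Interest are treated like serious ones. Section 7.8 ends reporting of Events of Clinical Interest earlier, "through 30 days following cessation of treatment".

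**Expected timing.** Section 4.5 says that immune-related events "may occur shortly after the first dose or several months after the last dose". Section 5.3.1 repeats this.

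**The concern.** The window to be analysed and the window in which anyone is scheduled to ask about AEs do not match. A report that follows sections 7.1 and 7.5.5 would present AE rates to 90 days after treatment. Under the calendar, active enquiry after the last dose stops at about day 28.

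This matters more for this drug class than for many others, because the protocol itself expects immune-related events months after dosing. Safety and toxicity are a stated secondary endpoint (section 1.2), and section 7.1 plans AE rates and laboratory toxicity grades. Table 7 marks no routine safety bloods after the day 28 visit, and thyroid tests are not marked even at that visit. A late, moderate, non-serious event would be recorded only if the patient or another physician reported it, or if someone happened to look.

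**Working it through.** The plan gives no figure to reproduce. The check is a day count on its own windows.

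**Inputs**
- End of the safety and capture window: day 90 (sections 7.1 and 7.5.5).
- Last AE assessment: day 28 ± 7, so day 21 to 35 (section 6.3, Table 7).
- Long-term contacts: 3 months ± 14 days after that visit, survival only (section 6.3, Table 7).
- Post-treatment scans: every 8 weeks ± 5 days, no AE item (section 6.3, Table 7 footnote E).
- Assumptions: the discontinuation date is the date of the last dose (day 0), and 3 months is 91 days.

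**Formulas**
- Days without a scheduled AE enquiry = 90 − day of the follow-up visit.
- First long-term contact = day of the follow-up visit + 91 ± 14.

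| Follow-up visit | Days without enquiry | Share of 90 days | First long-term contact |
|---|---|---|---|
| Day 21 | 90 − 21 = 69 | 77% | day 98 to 126 |
| Day 28 | 90 − 28 = 62 | 69% | day 105 to 133 |
| Day 35 | 90 − 35 = 55 | 61% | day 112 to 140 |

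Over all visit days, the first long-term contact falls between day 98 and day 140. Counting 3 months as 90 or 92 days widens this to day 97 to 141. In every case it comes after day 90.

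**Scans.** For a patient still being scanned, the nominal interval is 8 × 7 = 56 days. That is shorter than the 62-day gap, so with nominal timing at least one scan attendance falls inside it. With the ± 5-day margins, two scans can lie up to 56 + 5 + 5 = 66 days apart, so this is likely but not guaranteed. Scans stop at progression or new therapy, and progression is the first reason for ending treatment in section 4.7. Many patients who stop will therefore have no scan in the gap; the documents do not say how many.

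**Events of Clinical Interest.** Section 7.8 stops at 30 days. Section 7.5.4 handles such events like serious ones, and its window for those is 90 days or new therapy. It does not state 90 days for Events of Interest in so many words, so the conflict is an inference from reading the two sections together.

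**The case against.** The strongest case against the point has four parts.

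- **A capture rule already exists.** Section 7.5.5 obliges the site to capture new AEs to day 90, and section 7.5.4 obliges it to report serious ones, subject to the cut at new therapy. Related serious events outside that window are reportable too. This stands, and it narrows the point: what is missing is a scheduled prompt, chiefly for non-serious and laboratory-detected events. A duty to record what is noticed is not the same as asking.
- **Section 7.1 calls for a short focused history at each visit.** This could be read to cover scan attendances. But neither section 6.3 nor Table 7 attaches an AE assessment to those scans, and patients who have progressed or changed therapy do not have them.
- **A contact after day 90 can still record an earlier event retrospectively.** True, and section 6.3 lets those contacts use telephone, records or clinic visits. The valid criticism is that AE enquiry is not among their listed content.
- **Safety is descriptive here**, with no decision rule attached, and AEs are assessed every 2 weeks on treatment. This limits the consequence but does not reconcile the two windows.

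A reader might also infer that sections 7.1 and 7.5.5 are wrong to start at first dose, because section 7.5.4 starts at consent and some melanoma patients have craniotomy or LITT in between. The documents do not support that. The objective is the safety of MK-3475, sections 11.3 and 11.4.1 tie toxicity evaluability to receipt of the drug, and surgical events before the first dose are not drug toxicity. Serious events from consent are already reportable under section 7.5.4.

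**Conclusion.** The mismatch is real and can be read directly from the current text. With the visit on day 28, 62 of the 90 post-treatment days (69%; 55 to 69 days over the visit margin) carry no scheduled AE enquiry. This takes the last dose as the discontinuation date; if discontinuation is dated later, the section 7.1 window ends later and the gap is longer.

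Two stronger readings should be resisted. First, the 69% is a share of calendar days, not of events. The documents give no rate or onset pattern for late events, so under-counting is the expected direction but not a computed amount. Second, it is not true of every patient that the next contact concerns survival only; that holds for those who have progressed or started new therapy.

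The conflict over Events of Clinical Interest is secondary. Section 7.8 lists only two such events, an overdose without symptoms or abnormal laboratory results and a defined hepatic laboratory pattern, and a late hepatic event that came to notice would still be an AE under section 7.5.5.

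The point should be corrected because, followed as written, AE rates labelled as 90-day rates would rest on about 28 days of scheduled enquiry after the last dose.

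**What to change.** 1. Add an AE enquiry at about day 90 after the last dose to section 6.3 and mark it in Table 7. A telephone call is enough. It should ask about symptoms, treatment received elsewhere and outside laboratory results, because a call cannot detect an asymptomatic laboratory change.
2. Mark AE assessment in Table 7 at the 8-weekly post-treatment scan visits.
3. State whether the AE window ends at new anti-cancer therapy, as section 7.5.4 has it for serious events and sections 7.1 and 7.5.5 do not, and clarify how the alternative end in section 7.1 (resolution of acute toxicities) works with the 90 days.
4. Reconcile the 30-day window in section 7.8 with section 7.5.4.
5. Leave the start of the drug-safety analysis at first dose.

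The cost is a calendar amendment and about one call per patient: 20 + 44 + 10 = 74 at full enrolment, fewer if some patients die or withdraw first. The scan visits are already planned, so the added AE question needs no extra attendance. Sample size, response analysis and treatment rules are unaffected.
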